8.2.4. Analysis of Safety Data

Patients in Monotherapy Cohort will be analyzed by dose level and regardless of them. Patients in Combination Cohort will be analyzed separately as Combination Cohort 1 (Unfit Patients), Combination Cohort 2 (Fit Patients) and Combination Cohort 3 (Azacitidine Combination).

8.2.4.1. Adverse Events

Analysis set: Safety Analysis Set.

Table produced by: dose level and cohort. For the Continuation Cohort, only the listings will be produced.

Analysis:

The focus of AE summaries will be on Treatment Emergent Adverse Events, those with initial onset or increasing in severity after the first dose of study medication. See [Section 6.2.2](#) for the definition of treatment emergent adverse event. The number and percentage of patients who experienced any AE, serious AE (SAE), treatment related AE, and treatment related SAE will be summarized according to worst toxicity grades. The summaries will present AEs both on the entire study period and by cycle (Cycle 1 and Cycles beyond 1). For the summaries of AEs occurring at Cycles beyond 1, only the patients who start the study treatment of Cycle 2 will be analyzed.

Table:

Every table as described below will be created for any AE and treatment related AE.

- Discontinuations due to AEs;
- Temporary discontinuations or dose reductions due to AEs;
- Overall summary of AEs;

- Number of patients observed with AEs and corresponding percentages by MedDRA system organ class and preferred term;
- Number of patients observed with AEs and corresponding percentages by MedDRA preferred term sorted by frequency;
- Summary of death (Frequency of subject who died on-treatment, subject who died during follow-up, and cause of death).

Listings:

- AEs (all grade, and grade 3 and greater);
- Death;
- SAE.

8.2.4.2. Laboratory Tests

Analysis set: Safety Analysis Set.

Table produced by: dose level and cohort. For the Continuation Cohort, only the listings will be produced.

Analysis:

The number and percentage of patients who experienced laboratory test abnormalities will be summarized according to worst toxicity grade observed for each laboratory assay. The summary and shift summary of baseline grade by maximum post-baseline CTCAE grade will be presented. For laboratory tests without CTCAE grade definitions, results will be categorized as normal, abnormal or not done.

Tables:

- Summary results by maximum CTCAE grade;
- Shift summary results of baseline grade by maximum post-baseline CTCAE grade;
- Worst on-study abnormality.

Figure:

Individual values will be plotted over time for each continuous laboratory parameters by dose level and cohort as data allow.

Listings:

- Measured data;
- NCI-CTCAE grades;

- Measured data with NCI-CTCAE grades 3 and 4;
- Abnormality records (by subject, by test).

8.2.4.3. Hy's Law

Analysis set: Safety Analysis Set.

Table produced by: Not applicable.

Analysis: The subjects will be identified as potential Hy's Law cases based on Protocol Section 8.6.2.

Tables: Not applicable.

Figure: Not applicable.

Listings: Listing includes baseline values, actual value, ULN, and ratio of actual value to ULN with flag indicates the result meets the Hy's law criteria for each laboratory test (bilirubin, AST, ALT, and alkaline phosphatase) by study day measured laboratory test. Listing will be produced by dose level, cohort and malignancy.

8.2.4.4. Analysis of ECG

Analysis set:

(1) QTc-evaluable Analysis Set; (2) Safety Analysis Set

Table produced by: dose level, cohort. For the Continuation Cohort, only the listings will be produced.

Analysis:

ECG measurements (an average of the triplicate measurements) will be used for the statistical analysis (duplicate ECGs will also be averaged and single ECGs used if necessary). Any data obtained from ECGs repeated for safety reasons after the nominal time-points will not be averaged along with the preceding triplicates. Interval measurements from repeated ECGs will be included in the outlier analysis as individual values obtained at unscheduled time points. The average of triplicate or duplicate measurements will be rounded off and handle as integer in the analyses of ECG.

Descriptive statistics (n, mean, median, standard deviation, minimum, and maximum) will be used to summarize the absolute QTc, QT, HR, PR, QRS values and changes from baseline in QTc, QT, HR, PR, QRS by treatment arm, cohort and time point. For each patient and by treatment, the maximum increase from baseline as well as the maximum post-baseline value will be calculated across time points using the correction method(s) deemed appropriate. Categorical summarization of the QTc (using the most appropriate correction method), QT, HR, PR, QRS data will be conducted and summarized as follows:

- *The number of patients with maximum increase from baseline in QTc (<30, ≥ 30 - < 60 , and ≥ 60 msec);*
- *The number of patients with maximum post-dose (post-baseline) QTc (<450, ≥ 450 - ≤ 480 , ≥ 481 - ≤ 500 , and ≥ 501 msec);*
- *PR changes from baseline $\geq 25\%$ and baseline absolute values over >200 msec, or PR changes from baseline $\geq 50\%$ and baseline absolute values over ≤ 200 msec;*
- $PR \geq 300$ msec;
- *QRS changes from baseline $\geq 25\%$ and baseline absolute values over >110 msec, or QRS changes from baseline $\geq 50\%$ and baseline absolute values over ≤ 110 msec;*
- $QRS \geq 200$ msec.

Shift tables will be provided for baseline vs. worst on study QTc (one or more correction methods may be used) using the categories described above.

Tables:

- Descriptive statistics of absolute values by time point [analysis set (1) and (2)];
- Descriptive statistics of change from baseline values by time point [analysis set (1)];
- Descriptive statistics of maximum post-baseline values [analysis set (1)];
- Descriptive statistics of maximum increase from baseline values [analysis set (1)];
- Categorical summary of post-baseline maximum absolute values [analysis set (1) and (2)];
- Categorical summary of maximum increase from baseline values [analysis set (1)];
- Shift summary of QTcF results [analysis set (1)].

Listings:

- Measured data (QT, HR, PR, QRS and QTcF);
- Change from baseline (QT, HR, PR, QRS and QTcF);
- Qualitative results;
- Maximum values (QT, HR, PR, QRS and QTcF);
- Maximum change from baseline (QT, HR, PR, QRS and QTcF).

8.2.5. Analyses of Vital Signs

Analysis set: Safety Analysis Set.

Table produced by: dose level and cohort. For the Continuation Cohort, only the listings will be produced.

Table: Not applicable.

Figure:

For actual measures and changes from baseline, individual plot will be created for each vital sign as data allow. Actual time from Cycle 1 Day 1 will be used as X-axis in unit of day.

Listing:

Listing will be prepared for each vital sign, and will include actual measures, change from baseline and both met the specific categories (see [Appendix 1](#)).

8.2.6. Analysis of PK Data (excluding the Continuation Cohort)

8.2.6.1. Pharmacokinetic Parameters [excluding the Expansion Cohort of LDAC combination for efficacy (Unfit Patients)]

Analysis set: PK Parameter Analysis set

Each PK parameter will be summarized wherever applicable. The set of summary statistics as specified in the table below will be included:

Parameter	Summary statistics
AUC, C _{max} , C _{min} , C _{avg} , C _{trough} [*] , CL (CL/F), Vz (Vz/F)	N, geometric c mean, median, geometric CV%, standard deviation, minimum, maximum, arithmetic mean
T _{max} , R _{ac} , R _{ss}	N, median, minimum, maximum
t _{1/2}	N, arithmetic mean, median, CV%, standard deviation, minimum, maximum.

* C_{trough} is defined as the observed concentration prior to dose administration.

These summary tables will be generated by analyte for the PK analysis set. The PK parameters generated will be summarized by cohort, analyte, dose, cycle and day.

C_{trough} will be summarized separately for each cohort. Additionally, summaries will be generated for ONLY patients that received PF-04449913 daily without interruptions or dose reductions 6 days prior to the day of sample collection.

- Box and whisker plots for individual subject parameters by analyte (AUC, C_{max} and C_{trough} , CL/F, Vz/F) and overlaid with geometric means will be presented for the PK analysis set and for ONLY patients that received PF-04449913 daily without interruptions or dose reductions 6 days prior the day of sample collection.
- A listing of PK parameters by cohort, analyte, dose cycle, and day.

8.2.6.2. Pharmacokinetic Concentrations

Analysis set: PK Concentration Analysis set

- A listing of daily dosing including dose modification status and day as appropriate for each cohort by analyte.
- A listing of all plasma concentrations sorted by cohort, analyte, dose, cycle, day and nominal time post dose. The listing of plasma concentrations will include the actual times. Deviations from the nominal time will be given in a separate listing.
- A summary of plasma concentrations by cohort, analyte, dose, cycle, day and nominal time post-dose, where the set of statistics will include n, mean, median, standard deviation, coefficient of variation (% CV), minimum, maximum and the number of concentrations above the lower limit of quantification for the PK analysis set. Plasma concentrations by cohort, analyte, dose, cycle, day and nominal time post-dose, will be reported also for ONLY patients that are considered dose compliant (steady state with respect to that analyte).
- Median plasma concentrations time plots (on both linear and semi-log scales) against nominal time post-dose by analyte and dose for the PK analysis set and for ONLY patients that are considered dose compliant (steady state with respect to that analyte).
- Individual plasma concentration time plots by analyte and dose (on both linear and semi-log scales) against actual time post-dose.
- Individual C_{trough} plasma concentration time plots for PF-04449913 (on linear scales) against Cycle/Day.

8.2.7. Analysis of Drug-Drug Interaction (Combination Cohorts 1, 2, 3 Only)

8.2.7.1. Unfit Cohort: PF-04449913 and LDAC

The primary pharmacokinetic parameters, AUC and C_{max} , will be utilized to estimate the effect of co-administration of PF-04449913 and LDAC on the pharmacokinetics of either PF-04449913 or LDAC. The geometric mean ratios and its 90% confidence intervals (if data permit) for the PK parameters will be used for assessment of the extent of interaction for PF-04449913 in presence of LDAC and PF-04449913 alone.

PF-04449913 AUC and C_{max} when administered alone (Cycle 1/Day 21) will be compared to Cycle 1/Day 10 AUC and C_{max} , when administered in combination with LDAC. A similar assessment will be performed to determine the effect of PF-04449913 on LDAC. The AUC and C_{max} on Cycle 1 Day 2 when LDAC is administered alone will be compared to Cycle 1/Day 10 AUC and C_{max} when administered in combination with PF-04449913.

8.2.7.2. Fit Cohort: PF-04449913 and Daunorubicin/Cytarabine

The primary pharmacokinetic parameters, AUC and C_{max} , will be utilized to estimate the effect of co-administration of PF-04449913 and daunorubicin/cytarabine on the pharmacokinetics of PF-04449913. The geometric mean ratios and its 90% confidence intervals (if data permit) for the PK parameters will be used for assessment of the extent of interaction for PF-04449913 in presence of daunorubicin/cytarabine and PF-04449913 alone.

PF-04449913 AUC and C_{max} when administered alone (Induction Cycle Day 10) will be compared to Induction Cycle/Day 3 AUC and C_{max} , when administered in combination with daunorubicin/cytarabine. The effect of PF-04449913 on daunorubicin/cytarabine will not be conducted within the study due to the inability to dose daunorubicin/cytarabine alone.

8.2.7.3. Azacitidine Combination Cohort: PF-04449913 and Azacitidine

The primary PK parameters, AUC and C_{max} , will be utilized to estimate the effect of co-administration of PF-04449913 and azacitidine on the PK of either PF-04449913 or azacitidine. The geometric mean ratios and its 90% confidence intervals (if data permit) for the PK parameters will be used for assessment of the extent of interaction for PF-04449913+ azacitidine vs. PF-04449913 alone. A similar assessment will be conducted for azacitidine + PF-04449913 vs. azacitidine alone.

PF-04449913 AUC and C_{max} when administered alone (Cycle 1/Day 21) will be compared to Cycle 1/Day 7 AUC and C_{max} , when administered in combination with azacitidine. A similar assessment will be performed to determine the effect of PF-04449913 on azacitidine. The AUC and C_{max} on Cycle 1 Day 1 when azacitidine is administered alone will be compared to Cycle 1/Day 7 AUC and C_{max} when azacitidine is administered in combination with PF-04449913.

8.2.8. Analysis of PD Biomarker Data (excluding the Continuation Cohort)

PD biomarkers will be assessed separately for blood, serum, normal skin biopsies, bone marrow aspirate and bone marrow biopsies. In each case, summaries of baseline levels, changes from baseline (where appropriate), and mutation status will be reported. Summary statistics may include the mean and standard deviation, median, %CV and minimum/maximum levels of biomarker measures or frequency statistics, as appropriate. Data from biomarker assays will be analyzed using graphical methods.

If data permit, data from biomarker assays will be analyzed using graphical methods and descriptive statistics such as linear regression, Wilcoxon and ranked sum. Moreover, the statistical approach may examine correlations of biomarker results with pharmacokinetic parameters and measures of anti tumor efficacy.

Analysis set: PD Analysis Set.

Table produced by: dose level, cohort and biomarker type (plasma and cells).

Analysis:

Summaries of baseline and change from baseline (screening) to post-treatment as measured using ratio to baseline will be provided by time point. Graphical displays will be provided, as appropriate. All data will be listed.

For Combination Cohort 2 (Fit patients), summaries will be done separately for the induction, consolidation and maintenance periods, as well as together across periods. When summaries will be done separately for periods, the baseline in each period will be defined as the pharmacodynamic biomarker assessments on the first dosing day of study treatment in each period.

Tables:

- Summaries of actual value from baseline to post-treatment;
- Summaries of change from baseline (screening) to post-treatment by ratio to baseline.

Figure:

Individual plot will be plotted over time for each biomarker by dose level and cohort as data allow.

Listings: Each PD biomarker data will be listed.

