1.2.8.3. Clinical PD Summary

Analysis of Hh pathway gene expression changes in surrogate tissue (skin) in samples collected from both the B1371001 and B1371002 studies indicated >80% down regulation of the expression of the Hh pathway gene *GLI1* at doses of 80 mg or higher. To investigate PD data at doses lower than 80 mg, lower dose levels (such as 25 mg) may be explored at any time during the B1371005 study. Evaluation of circulating cytokine modulation demonstrated a post-treatment decrease in IL-8 and IL-10 in one MF patient who responded to treatment in B1371001, although limited conclusions can be drawn due to the small number of samples available for analysis. No consistent changes in cytokine levels were identified in patients treated in the B1371002 trial.

1.2.9. Rationale for the Starting Dose and the Highest Dose of PF-04449913 in This Trial

The Phase 1 study of single-agent PF-04449913 in select hematologic malignancies (B1371001) in Western patients has been completed. A total of 47 patients were treated at doses ranging between 5-600 mg daily. This study has identified the MTD as 400 mg QD in Western patients, and it was decided that the appropriate recommended phase 2 dose (RP2D) for PF-0449913 would be 200 mg or less, based on the following factors:

- Doses of PF-04449913 up to 200 mg are safe and well-tolerated following prolonged administration (most patients tolerated study drug for a minimum of 3 cycles in the dose range of 5-180 mg). Three patients (1 patient in the 400 mg group and 2 patients in the 600 mg group) had a post-baseline maximum QTcF interval of ≥ 500 msec;
- The most commonly reported treatment-related AEs have been grade 1 and 2, suggesting that PF-04449913 is generally well-tolerated. Most frequently reported treatment-related AEs include gastrointestinal-related events (weight loss, nausea, and diarrhea), dysgeusia, and muscle cramps;
- Clinical responses have been observed in 16 patients (including 5 patients with AML) with doses of PF-04449913 as low as 10 mg QD, with the majority of responses observed at 80 mg QD;
- Linear dose-dependent PK have been observed at all doses of PF-04449913 for which data are available, suggesting that exposures of PF-04449913 are predictable;
- *GLII* (a biomarker of Hh pathway signaling activation) expression is down-regulated by $\geq 80\%$ at doses of 80 mg QD or more in surrogate (skin) tissue, suggesting that at the 100 mg dose, there will be adequate target modulation.

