9.4.1.5. Statistical Analysis of Biomarker Endpoints

PD biomarkers will be assessed separately for blood, serum, normal skin biopsies and the bone marrow samples. In each case, summaries of baseline levels, changes from baseline (where appropriate), and mutation status will be reported. Summary statistics may include the mean and standard deviation, median, %CV and minimum/maximum levels of biomarker measures or frequency statistics, as appropriate. Data from biomarker assays will be analyzed using graphical methods and descriptive statistics such as linear regression, Wilcoxon and ranked sum. The statistical approach may examine correlations of biomarker results with pharmacokinetic parameters and measures of anti tumor efficacy.

Due to the exploratory nature of the proposed biomarkers, the data analysis will be conducted with the goal of identifying biomarkers with the strongest concordance to clinical outcome, encompassing both safety and efficacy. Candidate biomarkers will be validated in subsequent trials.

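### PD change is summarised as a raw ratio to baseline with arithmetic statistics; a geometric mean ratio would avoid a noise-dependent understatement of suppression

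*SAP*

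**What the plan says.** SAP 8.2.8 defines the PD change measure: "Summaries of baseline and change from baseline (screening) to post-treatment as measured using ratio to baseline will be provided by time point". The matching table entry is "Summaries of change from baseline (screening) to post-treatment by ratio to baseline". Tables are split by dose level, cohort and biomarker type.

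On statistics, the section says "Summary statistics may include the mean and standard deviation, median, %CV and minimum/maximum levels of biomarker measures". SAP 8.1.3, the general rule for continuous data, gives the same arithmetic set. Neither section mentions a log transformation, geometric mean or geometric CV for PD. By contrast, SAP 8.2.6.1 gives geometric means and geometric CVs for PK exposure parameters, and SAP 8.2.7.1 to 8.2.7.3 use geometric mean ratios with 90% confidence intervals for drug interaction.

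On further analysis, SAP 8.2.8 adds, only if data permit, "descriptive statistics such as linear regression, Wilcoxon and ranked sum". Protocol 9.4.1.5 has the same list. Neither gives the form of the Wilcoxon analysis, its scale, its null value or a significance level.

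**The concern.** Gene-expression and protein levels usually vary multiplicatively, so a halving and a doubling are equal and opposite changes. On the raw ratio scale they become 0.5 and 2.0, which average 1.25. A mean of raw ratios therefore drifts upwards, away from suppression, and drifts further when the assay or tissue is noisier.

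This matters because the size of suppression is the PD question. Protocol 1.2.8.3 gives the reference: GLI1 in skin was down-regulated by more than 80% at 80 mg or above. It continues: "To investigate PD data at doses lower than 80 mg, lower dose levels (such as 25 mg) may be explored". Up to 3 patients at 25 mg were added for this purpose (Protocol 3.1.1). If noise differs between dose levels or tissues, the same true suppression gives different mean ratios, and a difference in noise can look like a difference in effect.

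**Working it through.** The plan states no PD sample size, variance or power, so there is no stated figure to reproduce.

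**Direction, without a distributional assumption.** Let R be post/baseline. If nothing changes and the two measurements are exchangeable, R and 1/R have the same distribution. Then E[R] = E[(R + 1/R)/2]. Since R + 1/R is never below 2, E[R] is at least 1, with equality only if R is always exactly 1.

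**Size, under an assumption.** Take log R as normal with mean log(GMR) and SD σ, where GMR is the true geometric mean ratio. Then E[R] = GMR × exp(σ²/2). The suppression read from the arithmetic mean is 1 − E[R]. The documents give no σ, so a range is shown. At σ = 1.0 and GMR = 0.20, for example, 0.20 × exp(0.50) = 0.20 × 1.649 = 0.330, which reads as 67.0% suppression.

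| σ (SD of log ratio) | Mean ratio, no change | True 80% reads as | True 50% reads as |
|---|---|---|---|
| 0.2 | 1.02 | 79.6% | 49.0% |
| 0.3 | 1.05 | 79.1% | 47.7% |
| 0.5 | 1.13 | 77.3% | 43.3% |
| 0.8 | 1.38 | 72.5% | 31.1% |
| 1.0 | 1.65 | 67.0% | 17.6% |

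Two groups with the same true 80% suppression, one at σ = 0.3 and one at σ = 1.0, would differ by 79.1 − 67.0 = 12.1 points in the mean-based reading.

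**Does sample size help?** The expectation of the arithmetic mean does not depend on n. The sample geometric mean has expectation GMR × exp(σ²/(2n)), so its upward error shrinks as n grows. At n = 6 and σ = 1.0 the factor is exp(1/12) = 1.09, against 1.65 for the arithmetic mean. At n = 3 it is exp(1/6) = 1.18. The sample median also does better: under no change its average at n = 6 is 1.01 to 1.15 for σ from 0.3 to 1.0.

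**Would a test be affected?** Only if a one-sample signed-rank test were run on the raw ratio minus 1. At a two-sided 5% level:

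- At n = 3, 4 and 5 the smallest possible p-values are 2/8 = 0.25, 2/16 = 0.125 and 2/32 = 0.0625, so rejection is impossible on either scale.
- At n = 6 rejection requires all six changes to have the same sign. Size (2/64 = 3.1%) and power are therefore identical on the raw and log scales.
- At n = 15 (the Expansion Cohort), simulated size on the raw ratio is 5.2% to 9.1% for σ from 0.3 to 1.0, against about 4.8% on logs. Power for a true 50% decrease is 98.4% against 99.8% (σ = 0.5), 64.3% against 85.7% (σ = 0.8) and 39.6% against 67.8% (σ = 1.0).

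A rank-sum comparison between groups gives the same p-value on both scales, because the log does not change ranks.

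**The case against.** A reader might infer that the SAP tests the raw ratio against 1 and that its PD tests are therefore invalid. The documents do not support this. SAP 8.2.8 ties the ratio to summaries and a table. The Wilcoxon wording sits in a separate, conditional paragraph and may simply mean the rank-sum test, which is unaffected. The skin biopsies behind the GLI1 benchmark are taken only in the Monotherapy Cohort and Combination Cohorts 1 and 2 (Protocol 7.4.1.2). These have up to 3 patients at 25 mg, 3 to 6 per dose level otherwise, and 6 per combination cohort. At those sizes a two-sided 5% signed-rank test is the same on either scale.

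A reader might also infer a much larger bias by treating the baseline and post-treatment samples as independent with a high CV each. With per-sample log-SD s and within-patient correlation r, the factor is exp(s²(1 − r)). At s = 0.9 a true 80% suppression reads as 55% if r = 0 but 70% if r = 0.5. The documents give neither s nor r, so the larger figure cannot be asserted.

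Other points on this side stand in part. The list of statistics is permissive and attached to biomarker levels, not expressly to the ratio; however, it is the only list in the section, and SAP 8.1.3 repeats it as the general rule. The median, individual plots and full listings are planned, and with 3 patients every value will be visible. Protocol 1.2.8.3 does not say which average lies behind its 80% figure. PD is exploratory (Protocol 9.4.1.5), and no decision rule in SAP 4.2 uses it. These points lower the stakes. They do not make the arithmetic mean a good summary of a ratio.

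**Conclusion.** The point holds for the summary statistics. The arithmetic mean ratio is centred above 1 when nothing changes, and a mean-based reading understates suppression. At an assumed σ of 0.3 the loss is about 1 point at a true 80% suppression and about 2 points at 50%. At σ = 1.0 it is 13 and about 32 points. The direction needs only exchangeability under no change; the size rests on a log-normal ratio and an assumed σ.

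No fault in a planned test is shown. A test effect would arise only if a one-sample signed-rank test were run on the raw ratio in the Expansion Cohort or in pooled groups. This is a cheap improvement to a descriptive analysis and does not threaten the trial's primary conclusions.

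**What to change.** In SAP 8.2.8, for the ratio-to-baseline table, replace the arithmetic mean, SD and %CV with the geometric mean ratio, its back-transformed confidence interval where n allows, and the geometric CV. Keep the median and range. State that any regression or one-sample signed-rank test of change from baseline uses the log ratio. This brings PD into line with the SAP's PK and drug-interaction sections.

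The cost is SAP wording and a log transform in the programs, with no new data. The real downside is values below quantification. The PK convention in SAP 7.3 sets these to zero, which cannot be logged, and SAP 7.5 has no equivalent rule for PD. With strong suppression and 3 patients, a substituted value could dominate a geometric mean. The SAP should therefore either state a substitution rule in advance or fall back to the median alone when such values occur.
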